##### 2) Survey period

Each time point from the start of Nesina treatment to 12 months after treatment (or treatment discontinuation)

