Appendix Observation Schedule

Survey period		Observation period						
		At patient enrollment	At start of treatment	1 months after treatment	3 months after treatment	6 months after treatment	12 months after treatment	At treatment discontinuation
Parameter								
Patient enrollment	Nesina prescription date	○						
	Patient ID Number	○						
	Patients initial	○						
	Sex	○						
	Birth date	○						
	Assessment of inclusion criteria / exclusion criteria	○						
At patient demographics	Diagnosis period of type 2 diabetes mellitus		○					
	Category of clinical practice		○					
	Hypersensitivity predisposition		○					
	Concurrent disease		○					
	Past medical history		○					
	Height		○					
	Smoking history		○					
	Drinking history		○					
	Presence or absence of serum creatinine within 1 month after the start of Nesina treatment, serum creatinine level (if serum creatinine present), and severity of renal impairment and rationale for the assessment (if serum creatinine absent).		○					
Details of treatment, etc	Status of Nesina treatment		← ○ →					○
	Status of concomitant medication treatment (hypoglycemic agents* / other than hypoglycemic agents)		← ○ →					○
	Status of compliance with Nesina			○	○	○	○	○
	Status of compliance with diet/exercise therapy		○	○	○	○	○	○
Laboratory/Observation Parameters, etc	Pulse rate, blood pressure		○	○	○	○	○	○
	Weight		○	○	○	○	○	○
	Laboratory values							
	• HbA1c (NGSP value)							
	• Fasting glucose							
	• Fasting insulin							
	• Fasting glucagon							
	• Fasting triglyceride							
	• Total cholesterol							
	• HDL-cholesterol							
	• LDL-cholesterol							
	• Serum creatinine		○	○	○	○	○	○
	• BUN							
• Urinary albumin (corrected by creatinine)								
• AST								
• ALT								
• γ-GTP								
• ALP								
• Total bilirubin								
• Amylase								
• Lipase								
Electrocardiogram		○				○	○	
Waist circumference		○				○	○	
Tests for coronary arteriosclerosis and arteriosclerosis		○				○	○	
Pregnancy (yes or no) (females only)		← ○ →					○	
Adverse event		← ○ →					○	

○ To be performed

← ○ → To be performed throughout the period

\*Including hypoglycemic agents discontinued within 3 months before the start of Nesina treatment

**Protocol for  
Nesina Tablets Specified Drug-use Survey "Type 2  
Diabetes Mellitus: Combination Therapy With  
Hypoglycemic Drug (Insulin Preparation or  
Rapid-acting Insulin Secretagogues, Etc)"**

Version	Fifth version

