1.5 Handling of Laboratory/Measured Data

The evaluation time points for vital signs and laboratory tests will be at the start of Nesina treatment, 1 month, 3 months, 6 months, and 12 months after the start of Nesina treatment, and last evaluation.

The evaluation time points for electrocardiography, waist circumference, and coronary atherosclerosis and arteriosclerosis will be at the start of Nesina treatment, 12 months after the start of Nesina treatment, and last evaluation.

If multiple data exist within the relevant time point, calculate the absolute value of a difference in number of days from the reference number of days and select the minimum absolute value as the datum of the relevant evaluation time point. If the absolute values are same, select the datum at the latest examination/measurement day.

If "On treatment at 12 months after Nesina treatment" is selected in Section "Current Status of Nesina Treatment" in the survey sheet, all values will be used for analysis. If "On treatment at 12 months after Nesina treatment" is not selected, the values before the next day of the last administration of Nesina will be used for analysis.

The start day of Nesina treatment is defined as 0 days.

[Vital signs and laboratory test values]

Evaluation time point	Reference number of days	Lower limit of window	Upper limit of window
At start of Nesina treatment	0 days	30 days before Nesina treatment	Start day of Nesina treatment
1 month after start of Nesina treatment	30 days	1 day after start of Nesina treatment	60 days after start of Nesina treatment
3 months after start of Nesina treatment	90 days	61 days after start of Nesina treatment	136 days after start of Nesina treatment
6 months after start of Nesina treatment	180 days	137 days after start of Nesina treatment	273 days after start of Nesina treatment
12 months after start of Nesina treatment	360 days	274 days after start of Nesina treatment	456 days after start of Nesina treatment
At last evaluation	Select the latest datum from 1 to 456 days after the start of Nesina treatment		

[Electrocardiography and waist circumference]

Evaluation time point	Reference number of days	Lower limit of window	Upper limit of window
At start of Nesina treatment	0 days	30 days before Nesina treatment	Start day of Nesina treatment
12 months after start of Nesina treatment	360 days	1 day after start of Nesina treatment	456 days after start of Nesina treatment

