At last evaluation	Select the latest datum from 1 to 456 days after the start of Nesina treatment		

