5.19.3 Electrocardiography

(1) Patients to be tabulated and analyzed

Safety Analysis Set

(2) Details of tabulation and analysis

For assessment of electrocardiogram, cross tabulation will be used for the categories described below.

Total patients and patients who are taking concomitant insulin preparation, rapid-acting insulin secretagogues, SGLT-2 inhibitors, or other drugs will be tabulated.

Parameter	Category
ECG results at start of Nesina treatment	Clinical abnormal findings (Yes or No) or Not performed
ECG results at 12 months after start of Nesina treatment	Clinical abnormal findings (Yes or No) or Not performed
ECG results at last evaluation	Clinical abnormal findings (Yes or No) or Not performed

(3) Number of tables and figures

Table 5.19.3

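### The 12-month window for ECG and waist circumference opens on day 1, so a lone early reading is reported as a 12-month result

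*SAP*

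**What the plan says.** SAP section 1.5 counts the start day as day 0 and has two window tables.

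- **Vital signs and laboratory values.** There are four post-start windows: days 1–60, 61–136, 137–273 and 274–456. The 12-month row has reference day 360 and lower limit "274 days after start of Nesina treatment".
- **ECG and waist circumference.** The only scheduled post-start row is 12 months, with reference day 360, lower limit "1 day after start of Nesina treatment" and upper limit day 456. A further row for last evaluation reads "Select the latest datum from 1 to 456 days after the start of Nesina treatment".

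Two general rules in the same section apply to both tables. With several readings in a window, the analyst takes the one closest to the reference day ("select the minimum absolute value as the datum of the relevant evaluation time point"), and ties go to the later day. For a patient not recorded as on treatment at 12 months, "the values before the next day of the last administration of Nesina will be used for analysis".

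The ECG and waist limits are identical in SAP Versions 1 and 2. The outputs that use them are SAP 5.19.3, which has a row headed "ECG results at 12 months after start of Nesina treatment", and SAP 5.19.4, which gives waist summary statistics plus mean change from start with a 95% confidence interval.

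The protocol's Appendix Observation Schedule marks ECG and waist at the start, at 12 months and in the column "At treatment discontinuation". Protocol 9.2.5.3 and 9.2.5.4 likewise allow the follow-up reading to be taken at discontinuation.

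**The concern.** The same label and reference day carry two different meanings within one section. A visit in the second week can supply a 1-month weight and a 12-month waist circumference for the same patient.

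The patients concerned are foreseeable: those who stop early and are measured on or before the last dosing day, since the protocol asks for ECG and waist at discontinuation. Three things follow.

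- The 12-month n in SAP 5.19.3 and 5.19.4 may be overstated.
- The 12-month mean waist change and its interval can mix changes over days or weeks with changes over a year.
- An early ECG is counted as a finding (yes or no) at 12 months when no ECG was done near that time.

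The survey is meant to describe one year of use, so the time label matters to a reader.

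**Working it through.** **Inputs** (all from SAP 1.5): reference day 360; ECG/waist 12-month window days 1–456; vital-sign/laboratory 12-month window days 274–456; nearest-reading rule with ties to the later day; last evaluation = latest reading in days 1–456.

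**Window widths.**

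- ECG/waist: 456 − 1 + 1 = 456 days, from 359 days before day 360 to 96 days after it.
- Vital signs/laboratory: 456 − 274 + 1 = 183 days, from 86 days before to 96 days after.
- Difference: 456 − 183 = 273 days (days 1–273), and 273/456 = 59.9% of eligible days.

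**One usable reading.** In the other table those 273 days are split as 60 (1 month) + 76 (3 months) + 137 (6 months) = 273.

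| Only usable reading | Distance from day 360 | Label for weight or laboratory value | Label for ECG or waist |
|---|---|---|---|
| Day 14 | 360 − 14 = 346 | 1 month | 12 months |
| Day 100 | 360 − 100 = 260 | 3 months | 12 months |
| Day 200 | 360 − 200 = 160 | 6 months | 12 months |
| Day 274 | 360 − 274 = 86 | 12 months | 12 months |

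**Two usable readings, a < 274 ≤ b.** The earlier reading is chosen only if 360 − a < b − 360, that is a + b > 720. With b ≤ 456 this needs a ≥ 265, and with a ≤ 273 it needs b ≥ 448. Counting pairs from a = 273 down to a = 265 gives 9 + 8 + … + 1 = 45, out of 456 × 455 / 2 = 103,740 possible pairs of days. So the nearest-reading rule protects almost every patient who also has a reading on or after day 274. For example, readings on days 180 and 365 give day 365 under either window.

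**The other rule.** The on-treatment cut-off removes values after the last dosing day for patients not on treatment at 12 months. It leaves a reading taken on or before that day, however early.

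**12 months against last evaluation.** Both rows accept days 1–456, so any patient in one is in the other. With one post-start reading the two values are also identical, for every day from 1 to 456.

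**Consistency with SAP 4.0.** Treatment duration is tabulated there with cut-points at 60, 136, 273 and 455 days. A patient shown in that table as treated for 1–60 days can appear with a 12-month ECG or waist result.

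**The case against.** The strongest defence is that day 1 follows from the way the SAP builds its windows. The vital-sign and laboratory windows divide days 1–456 among four scheduled visits. ECG and waist have one routine post-start visit, so the same approach gives one window covering everything. Day 274 is simply the day after the 6-month window closes, and ECG and waist have no 6-month window. This may well be how the limit arose, and the SAP gives no reason either way. It does not make a change measured on day 14 a 12-month change, and last evaluation already exists to catch such readings.

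Several narrower points do stand.

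- The exposed group is limited: a reading on or before the last dosing day, before day 274, with nothing later. For waist change the patient also needs a baseline within the 30 days up to the start day. No ECG or waist is scheduled at 1, 3 or 6 months, so day 14 is an extreme example.
- The 59.9% is a share of calendar days and says nothing about the proportion of patients.
- These are peripheral descriptive outputs. Protocol section 10 names neither ECG nor waist among its safety or efficacy parameters, and SAP 5.19.3 and 5.19.4 include no hypothesis test.
- The SAP does not define the *Not performed* category for ECG. It may be a box on the survey sheet, which is not in the documents, so it is not certain that an early-only patient would otherwise fall there.

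**Conclusion.** The concern holds. As written, the rule labels any lone usable ECG or waist reading from days 1–273 as a 12-month result, and no other rule in the SAP removes it. The 12-month column therefore cannot show who was measured near 12 months.

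The size in patients is unknown: the documents give no discontinuation rate and no count of early readings, and the number may be small. That patients who stop early are the main source is an inference from the protocol's schedule. The effect is confined to the tables in SAP 5.19.3 and 5.19.4. HbA1c, other laboratory values and vital signs use days 274–456. It should be corrected because the label is wrong for these patients and the correction is trivial, although no main conclusion of the survey depends on it.

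**What to change.** In the ECG and waist circumference table of SAP 1.5, change the lower limit of the 12-month row from day 1 to day 274, matching the vital-sign and laboratory table. Earlier post-start readings then appear under last evaluation only.

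If the days 1–456 window was intended because only one routine follow-up is scheduled, say so in SAP 1.5. Rename the column in SAP 5.19.3 and 5.19.4 so that it does not claim 12 months.

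Either option should state how the ECG *Not performed* category is assigned: as recorded on the survey sheet, or whenever no reading falls in the window.

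The cost is one table cell or one column label, plus that one sentence. With the day-274 limit the 12-month n may be smaller, but no reading is lost.

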1.6 Display Data Digit

Display digits are described as below.

Term	Display digit	Unit
HbA1c (NGSP value)	0.1	%
Fasting blood glucose level	1	mg/dL
Fasting insulin level	0.1	μU/mL
Fasting glucagon	0.1	pg/mL
HOMA-R	0.1	—
HOMA-β	0.1	%
Fasting triglyceride	1	mg/dL
Total cholesterol	1	mg/dL
HDL-cholesterol	1	mg/dL
LDL-cholesterol	1	mg/dL
non-HDL cholesterol	1	mg/dL
Serum creatinine	0.01	mg/dL
BUN	0.1	mg/dL
Urinary albumin (corrected by creatinine)	0.1	mg/g•Cre
AST	1	IU/L
ALT	1	IU/L
γ-GTP	1	IU/L
ALP	1	IU/L
Total bilirubin	0.1	mg/dL
Amylase	1	IU/L

Term	Display digit	Unit
Lipase	1	IU/L
Waist circumference	0.1	cm
Pulse rate	1	bpm
Systolic blood pressure	1	mmHg
Diastolic blood pressure	1	mmHg
Weight	0.1	kg
BMI	0.1	kg/m ²
Age	1	Year
Duration of type 2 diabetes mellitus	0.1	Year
Height	1	cm
eGFR	0.1	mL/min/1.73 m ²
Nesina administration period	1	Day
Mean daily dose of Nesina	0.01	mg

2.0 Disposition of Patients (Patient Diagram)

(1) Patients to be tabulated and analyzed

Registered patients

(2) Details of tabulation and analysis

The following will be tabulated: the number of registered patients, number of medical site at which patients is registered, number of patients whose survey sheets are collected, number of patients whose survey sheets are not collected, number of patients in the Safety Analysis Set, number of patients in the Not Safety Analysis Set, number of patients in the Efficacy Analysis Set, and number of patients in the Not Efficacy Analysis Set.

For the number of medical sites at which patients are registered, do not duplicate the same medical site with different departments.

For patients whose survey sheets are not collected, tabulate the number of patients for each reason for not collected survey sheets.

For the Not Safety Analysis Set and Not Efficacy Analysis Set, the number of patients will be tabulated for each reason for exclusion to create the list.

The following is the handling of the decision whether patients who meet the following criteria should be evaluated:

Criterion	Safety evaluation	Efficacy evaluation
Pre-agreement administration [found after administration]	×	×
Registration 15 days after prescription of Nesina [found after registration]	×	×
Nesina taking not confirmed [after the end of patient registration period]	×	×
No data for post-administration of Nesina	×	×
Not using any of the 3 combination drugs (the treatment group will be classified as "Other.") (1) With insulin preparation (2) With rapid-acting insulin secretagogues (3) With SGLT-2 inhibitors	○	×

○ Included, × Excluded or not evaluated

(3) Number of tables and figures

Figure 2.0-1 and Table 2.0-1

3.0 Patient Demographics

(1) Patients to be tabulated and analyzed

Safety Analysis Set

(2) Details of tabulation and analysis

Each parameter will be classified by the categories described below to tabulate the number of patients and frequency.

Total patients and patients who are taking concomitant insulin preparation, rapid-acting insulin secretagogues, SGLT-2 inhibitors, or other drugs will be tabulated.

Parameter	Category
Sex	Male, Female
Age	Summary statistics
	< 65 years, ≥ 65 years
	< 75 years, ≥ 75 years
	< 20 years, 20 to 29 years, 30 to 39 years, 40 to 49 years, 50 to 59 years, 60 to 69 years, 70 to 79 years, ≥ 80 years
Disease duration of type 2 diabetes mellitus (year)	Summary statistics
	< 2 years, 2 to < 5 years, 5 to < 10 years, ≥ 10 years, Unknown
Height	Summary statistics
Category of clinical practice	Outpatient, Inpatient
Pregnancy (only females)	No, Yes
Severity of renal impairment	Normal, Mild, Moderate, Severe
	Normal + Mild, Moderate + Severe
Concurrent disease	No, Yes
Diabetic complication	No, Yes
Details of diabetic complication (overlapped)	Diabetic nephropathy, diabetic retinopathy, diabetic neuropathy For the proportion, the number of patients with diabetic complication will be denominator.
Concurrent hypertension	No, Yes
Concurrent dyslipidemia	No, Yes
Concurrent hyperuricemia	No, Yes
Concurrent liver disorder	No, Yes

Parameter	Category
Details of concurrent liver disorder (overlapped)	Hepatic steatosis, alcoholic hepatitis, chronic hepatitis, hepatic cirrhosis, or other For the proportion, the number of with concurrent liver disorder will be denominator.
Severity of hepatic impairment	Normal, Grades 1, 2, and 3, or Unknown
Concurrent renal disorder	No, Yes
Details of concurrent renal disorder (overlapped)	Nephrotic syndrome, glomerulonephritis, chronic glomerulonephritis, other For the proportion, the number of with concurrent renal disorder will be denominator.
Severity of renal impairment (eGFR)	Normal, Mild, Moderate, Severe, or Unknown
	Normal + Mild, Moderate + Severe, or Unknown
Severity of renal impairment (serum creatinine)	Normal, Mild, Moderate, Severe, or Unknown
	Normal + Mild, Moderate + Severe, or Unknown
Concurrent heart disease	No, Yes
Details of concurrent heart disease (overlapped)	Cardiac failure, myocardial infarction, angina pectoris, other For the proportion, the number of with concurrent heart disease will be denominator.
Concurrent cardiac failure	No, Yes
Severity classification of cardiac failure (NYHA classification)	Classes NYHA I, NYHA II, NYHA III, and NYHA IV, Unknown For the proportion, the number of with concurrent cardiac failure will be denominator.
Concurrent stroke-related disease	No, Yes
Details of concurrent stroke-related disease (overlapped)	Cerebral infarction, cerebral hemorrhage, subarachnoid hemorrhage, transient ischaemic attack For the proportion, the number of with concurrent stroke-related disease will be denominator.
Concurrent allergic disease	No, Yes
Concurrent malignant tumour	No, Yes
Concurrent malignant	No, Yes

Parameter	Category
tumour (narrow sense)	
Other concurrent disease	No, Yes
Past medical history	No, Yes, Unknown
Hypersensitivity predisposition	No, Yes, Unknown
Alcohol history (drinking alcoholic drinks almost on a daily basis)	Yes, No, Unknown
Smoking history	Never, Smoking, Smoked, Unknown
HbA1c (NGSP value) (at the start of Nesina treatment)	Summary statistics <hr/> < 6.0%, 6.0% to < 7.0%, 7.0% to < 8.0%, ≥ 8.0%, Unknown <hr/>
Weight (at the start of Nesina treatment)	Summary statistics
BMI (at the start of Nesina treatment)	Summary statistics <hr/> < 18.5 kg/m ² , 18.5 to < 25 kg/m ² , 25 to < 30 kg/m ² , ≥ 30 kg/m ² , Unknown <hr/> < 25 kg/m ² , ≥ 25 kg/m ² , Unknown <hr/>
Waist circumference (at the start of Nesina treatment)	Males: < 85 cm, ≥ 85 cm, or Unknown / Females: < 90 cm, ≥ 90 cm, or Unknown

(3) Number of tables and figures

Table 3.0-1

4.0 Details of Treatment

(1) Patients to be tabulated and analyzed

Safety Analysis Set

(2) Details of tabulation and analysis

Each parameter will be classified by the categories described below to tabulate the number of patients and frequency.

Total patients and patients who are taking concomitant insulin preparation, rapid-acting insulin secretagogues, SGLT-2 inhibitors, or other drugs will be tabulated.

Parameter	Category
Initial dose of Nesina	25 mg, 12.5 mg, 6.25 mg, or other
Mean daily dose of Nesina	> 25 mg, 25 to >12.5 mg, 12.5 to > 6.25 mg, or ≤ 6.25 mg
Nesina treatment period	Summary statistics
	1 to 60 days, 61 to 136 days, 137 to 273 days, 274 to 455 days, ≥ 456 days
Administration of prior medication (diabetic drug)	No, Yes, or Unknown
Prior medications (diabetic drugs)	
α-glucosidase inhibitors, thiazolidines, sulfonylureas, biguanides, rapid-acting insulin secretagogues, insulin preparations, DPP-4 inhibitors, GLP-1 receptor agonists, SGLT-2 inhibitors, combination of diabetic drugs, or other diabetic drugs
 
For the proportion, the number of patients with “Yes” for administration of prior medication (diabetic drug) will be denominator.

Administration of prior medication (other than diabetic drug)	No, Yes, or Unknown
Administration of concomitant medication (diabetic drug)	No, Yes, or Unknown
Concomitant medications (diabetic drugs) (overlapped)	
α-glucosidase inhibitors, thiazolidines, sulfonylureas, biguanides, rapid-acting insulin secretagogues, insulin preparations, DPP-4 inhibitors, GLP-1 receptor agonists, SGLT-2 inhibitors, combination of diabetic drugs, or other diabetic drugs
 
For the proportion, the number of patients with “Yes” for administration of concomitant medication (diabetic drug) will be

Parameter	Category
	denominator.
Administration of concomitant medication (hypertension drug)	No, Yes, or Unknown
Concomitant medications (hypertension drugs) (overlapped)	ARB, Ca antagonists, ACE inhibitors, diuretics, α blockers, $\alpha\beta/\beta$ blockers, complication of hypertension drugs, or other For the proportion, the number of patients with “Yes” for administration of concomitant medication (hypertension drug) will be denominator.
Administration of concomitant medication (dyslipidaemia drug)	No, Yes, or Unknown
Concomitant medications (dyslipidaemia drugs) (overlapped)	Statins, fibrates, EPA/DHA, or other For the proportion, the number of patients with “Yes” for administration of concomitant medication (dyslipidaemia drug) will be denominator.
Administration of concomitant medication (protease drug)	No, Yes, or Unknown
Administration of concomitant medication (combined with renal excretory drug)	No, Yes, or Unknown
Administration of concomitant medication (other)	No, Yes, or Unknown

(3) Number of tables and figures

Table 4.0-1

4.1 Compliance

4.1.1 Status of compliance with Nesina

(1) Patients to be tabulated and analyzed

Safety Analysis Set

(2) Details of tabulation and analysis

For the status of compliance with Nesina, the frequency will be tabulated at each testing time point (1 month, 3 months, and 6 months after the start of Nesina treatment and last evaluation or treatment discontinuation).

Total patients and patients who are taking concomitant insulin preparation, rapid-acting insulin secretagogues, SGLT-2 inhibitors, or other drugs will be tabulated.

Parameter	Category
Status of compliance with Nesina	≥ 90%, ≥ 70%, ≥ 50%, or < 50%

(3) Number of tables and figures

Tables 4.1-1

4.1.2 Status of Compliance with Diet Therapy

(1) Patients to be tabulated and analyzed

Safety Analysis Set

(2) Details to be tabulated and analyzed

For the status of compliance with diet therapy, the frequency will be tabulated at each testing time point (at the start of Nesina treatment, 1 month, 3 months, 6 months, and 12 months after the start of Nesina treatment and last evaluation or treatment discontinuation). The latest datum will be used for last evaluation.

Total patients and patients who are taking concomitant insulin preparation, rapid-acting insulin secretagogues, SGLT-2 inhibitors, or other drugs will be tabulated.

Parameter	Category
Status of compliance with diet therapy	≥ 90%, ≥ 70%, ≥ 50%, < 50%, Not performed, or Unknown

(3) Number of tables and figures

Table 4.1.2

